Counseling interventions received a grade B recommendation from the USPSTF (2), reflecting the low level of risk and high probability of a moderate net benefit. None of the included studies, however, offered virtual counseling and there is very little evidence of the efficacy of virtual prevention interventions. As in all studies where participants report on their mental health, there is always the possibility that participants become more aware of their symptoms. We will minimize risk to participants by taking the following measures. First, at the end of each assessment, there will be a list of resources to manage mental health issues (Appendix M). The list will include contact information for: 1) in Quebec, Integrated University Health and Social Services Centres (CIUSS). These local community health centers offer prenatal classes, telephone call services, and links to psychosocial and mental health services; 2) family physician clinics; 3) obstetric clinics, and; 4) emergency phone numbers and help lines. Second, we will set up a telephone line to answer questions about the study and remind participants of available resources. Third, participants with a positive response on the EPDS self-harm ideation item or scoring above the clinical EPDS cut-off (≥ 13) during screening or follow-up will be notified by a pop-up at the end of the questionnaire. The pop-up will inform them they will receive a phone call from a nurse of our team and encourage them to speak to their doctor and contact resource links (Appendix N). The nurse will make the call within 24 hours to evaluate the suicidal risk and make sure the participant is taken in charge by appropriate health services.

Expected Results and Benefits

[figure not shown]
This project will 1) provide virtual support related to the program content to women with symptoms of depression (moderate severity) in a context where individual medical and psychosocial follow-ups are minimized due to the pandemic; 2) prevent the worsening of depression and anxiety, improve stress management, and potentially improve obstetric outcomes and prevent child development disorders associated with maternal disorders; 3) develop an online economic intervention for pregnant women in situations of social isolation or activity limitations due to various causes (e.g., pandemic, strict rest at home); 4) facilitate the coordination of virtual social support by maternal and child physical health specialists and

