Pregnant women will be recruited via three possible means: 1) Recruitment posters and pamphlets (Appendix B, Recruitment poster and pamphlet) distributed in clinics associated with the CHU Ste Justine; 2) Obstetrician, psychiatrists or general practitioner in clinics associated with the CHU Ste Justine; or 3) Advertisements posted on various social media (Facebook, Instagram; Twitter, etc.). Interested women will either 1) connect to a web page and fill a contact form (Appendix C); or 2) contact us by phone, text message or email.

The research coordinator will contact women referred by practitioners or through advertisement. The study will be explained and a consent form (Appendix F, Consent forms) will then be sent through REDCap. Participants will sign virtually. Then, they will respond by telephone to the eligibility questionnaire (5 min.), including the EPDS (50) psychosis screening questionnaire and self reported substance abuse problem. Those with subclinical levels of depression (EPDS 9-12) and without psychosis and substance abuse problem will be randomized via REDCap and informed of their group allocation.

Partners Recruitment

During the recruitment phone call with pregnant women, the research coordinator will explain the possibility of partners to participate in the study and the advantage of it. A partner can be the spouse or any other significant person who will accompany the pregnant woman during pregnancy and after childbirth. It is recommended to keep the same person for the duration of the course. The research coordinator will ask the pregnant women to identify her partner and if he or she is at home at this moment, he or she will be invited to join the call. Partners will be eligible only if the pregnant woman signed the consent form and is eligible for the study. If the partner is absent, the research coordinator will ask for his or her email or telephone number. If the pregnant woman sign the consent form and is eligible for the study, an invitation will be sent to briefly explain the project and to ask them if they accept us to call them to give more information and recruit them if interested. The research coordinator will then contact those interested, explain the study and send an email with the consent form.

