Recruited pregnant women and partners will receive a notification with a link to answer the baseline questionnaire (Appendix E, Baseline and follow-up questionnaires) online and our contact information to take an appointment with a research assistant if they prefer to answer the questionnaire on the phone. After completion of the baseline questionnaire, access to the intervention website will be authorized.

[figure not shown]
Planned recruitment rate

The participant recruitment rate depends on two factors: 1) capacity to recruit pregnant women with subclinical depressive symptoms (EPDS 9-12); 2) participant acceptance of the trial. In one of our ongoing mental health studies in pregnant women, 374 (22.1%) participants with EPDS scores 9-12 (out of 1695 assessed) were recruited over social media in a two-week period (i.e., 185/week). Within Sainte Justine's obstetrics clinics, 25 – 30 women/week are assessed with the EPDS. Therefore, we expect to recruit around five women/week at the beginning of our trial. When we will expand our recruitment on social media, we estimate to recruit $n = 15$ women per week willing to accept randomization. The recruitment period should last a total of approximately ten months. Thus, an average of 25 women per month would enter the intervention under the guidance of one of 3 *coaches* (i.e., 8 women/*coach*). Intervention activities will take 18-20 months. Figure 2 presents the schedule of recruitment and intervention implementation.

Participating centers.

The trial is based at Sainte Justine Hospital (CHU Ste-Justine), the largest mother-child hospital in Quebec. Affiliated obstetric clinics will refer patients to the study site (Appendix G, Letters of Support). These clinics provide an ideal setting for recruiting mothers of diverse ethnic backgrounds.

Figure 2. Schedule of recruitment and intervention implementation

¹ First women to complete will begin the trial at 25 gestational weeks in the first wave of recruitment

² Last women to complete will begin the trial at 12 gestational weeks in the last wave of recruitment

Sample

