Duration of treatment period. The typical duration of the program is 2 months (8 weeks) during pregnancy and 2 months over the first 3 months of the baby's life. The two postpartum sessions aim to lend support during the challenges of the postpartum period. The proposed frequency of nurse telephone follow-up is once/week in pregnancy and once/month in postpartum, but this can be adapted to the needs of the woman and/or her partner. Figure 3 presents the intervention and assessments.

Figure 3. Frequency and duration of the follow-up

Participants will fill out questionnaires (online or by telephone) at T₀ (12-25 weeks' gestation), T₁ (3 months' postpartum), and T₂ (6-months postpartum) to assess baseline values and trial outcomes, respectively. If we show efficacy at 3 months' postpartum (primary outcome), we will seek funding to follow families over the early childhood years. Real date of birth will be assessed six weeks after the estimated date of birth.

Coaches training and supervision. PhD students in clinical psychology and Master's students in nursing are ideally suited to conduct the 10 follow-up calls. They will be supervised by our multidisciplinary team (2 nurses, 2 clinical psychologists, and 2 psychiatrists). All coaches will receive 5-day training in perinatal mental health and use of the intervention material. Procedures for calls will be outlined in the intervention manual. The supervision team will oversee implementation as part of the Executive Committee. Intervention sessions will be audiotaped and randomly reviewed by the supervision team to ensure compliance with the material.

Virtual intervention without telephone support (control group). The control group will receive a fully automated version of the virtual intervention

Data Collection

We will conduct a comprehensive assessment of perinatal maternal mental health and functioning as well as factors that may modify the impact of the intervention. The chosen assessment tools are validated (French and English), require low levels of literacy and take only 15-30 minutes to complete (Appendix L, Description of assessment tools). They have been used previously with pregnant women and examined for clarity, comprehension, and ease of use. The questionnaires will be completed online via REDCap or over the telephone with a research assistant blinded to group allocation depending on maternal preference, and with the partner if the woman so chooses.

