Primary outcome. Maternal depression at 3 months' postpartum was chosen as the primary outcome to: 1) ensure comparability to other perinatal trials (60-67) and 2) to reduce potential biases induced by attrition. The primary outcome will be the proportion of women with EPDS scores above the clinical cut-off for depression (EPDS \geq 13)). Differences between experimental and control groups will be analyzed at T₁ (3 months' postpartum) and again at T₂ (6 months' postpartum, secondary outcomes). The EPDS is an internationally recommended 10-item self-report scale that assesses depressive symptoms on a 4-point scale; scores range from 0 to 30 with higher scores representing higher symptomatology. More than 80% of perinatal depression studies use self-report measures (73) and the majority use the EPDS. The EPDS was created to counter the limitations of other well-established depression scales when used during the perinatal period. It has been validated by standardized psychiatric interviews with large sample sizes and has well-documented reliability and validity of over 11 languages (50, 74). Participants will fill out the EPDS at 3 assessment times: baseline (T₀, as part of inclusion criterion), T₁, and T₂.

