Secondary outcomes. Participant and partner assessments at baseline, T₁ and T₂. The proposed intervention is based on CBT principles used to treat both anxiety and depression. As anxiety is highly correlated with perinatal depression, it is an important secondary outcome. **Generalized anxiety.** The proposed intervention is based on CBT principles used to treat both anxiety and depression. As anxiety is highly correlated with perinatal depression, it is an important secondary outcome. Anxiety will be assessed at all 3 time points, using the Generalized Anxiety Disorder 7-item (GAD-7) scale, an extensively validated self-report instrument (75-77). **Anxiety related to pregnancy** will be measured with the 10-item Pregnancy-specific anxiety scale (PRAQ-R2) (78, 79) at baseline. **Stress** will be assessed using the 10-item form of the Perceived Stress Scale, at six months postpartum (80, 81). **Well Being** will be evaluated with the 5-item WHO-5 well-being index at T₁ (82). **Self-efficacy** will be assessed using the 10-item General Self-Efficacy Scale (GSE) at 3 months postpartum (83, 84). **Self-Compassion** will be measured with the 12-item shortened version of the Self-Compassion Scale (SCS) (85-87), at 3 months postpartum. **Sleep.** Sleep may improve as a result of the increased capacity for relaxation, mindfulness, and emotional regulation fostered by the intervention. At 3 months postpartum, we will assess sleep quality, a critical aspect of perinatal maternal health, using the 19-item Pittsburgh Sleep Quality Index (PSQI) (88, 89), a self-report over a one-month interval with very good psychometric properties and validated for use during postpartum (90). **Tobacco, alcohol and drug use** will be self-reported at baseline and 3 months postpartum. **Social Adjustment** will be assessed using the 14-item screener version of the Social Adjustment Scale – Self-report (SAS-SR) (91, 92). Six major areas are covered: work (paid or unpaid), social and leisure activities, relationships with extended family, role as marital partner, role as a parent, and role within the family unit (including perceptions about economic functioning). For this study, we will only use the work subscale at 3 months postpartum. **Marital satisfaction** will be evaluated with the short version of the Dyadic Adjustment Scale (DAS-7) (93-95) at 3 months postpartum. **Co-parenting.** The proposed intervention is partner-inclusive and, as such, may improve co-parenting quality (the extent to which parents work together and agree on childcare and education). We will use a brief 14-item version of the Coparenting Relationship Scale (75) (e.g., partner pays a great deal of attention to our child; partner appreciates how hard I work at being a good parent) at 3 months postpartum. **Social Support** will be assessed at 6 months postpartum using the 10-item Social Provisions Scale (SPS-10) on emotional

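### As the prose reads, women learn their arm before most of T0 is completed, which could touch GAD-7, added covariates and partner uptake but not the primary test; separately, the gender-role moderator is built from T2 data

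*Combined protocol and SAP*

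**What the plan says.** Pregnant Women Recruitment describes consent, then a short telephone eligibility questionnaire (EPDS, psychosis screen, self-reported substance abuse). Women in the EPDS range and "without psychosis and substance abuse problem will be randomized via REDCap and informed of their group allocation".

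The text under Partners Recruitment closes with the baseline step: "Recruited pregnant women and partners will receive a notification with a link to answer the baseline questionnaire". It continues: "After completion of the baseline questionnaire, access to the intervention website will be authorized". A partner who is at home may join the recruitment call. An absent partner is invited once the woman has consented and is eligible, and consents later.

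Primary outcome states: "Participants will fill out the EPDS at 3 assessment times: baseline (T₀, as part of inclusion criterion), T₁, and T₂". Under Secondary outcomes, the lead line reads "Participant and partner assessments at baseline, T₁ and T₂", but the scales are then given individual times. GAD-7 is taken at all three points and PRAQ-R2 at baseline only. Most other scales are taken once, at 3 or 6 months.

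Planned Analyses tests the primary outcome with an unadjusted chi-square. The supplementary ANCOVA names baseline EPDS as covariate. Continuous secondary outcomes use ANCOVA by reference back to that model. Baseline variables found unbalanced may be added, for primary as well as secondary outcomes.

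The tertiary research question lists gender, measured at baseline, as a moderator. Under Other variables (effect modifiers), the gender-role score for women and partners is built from T2 data, including employment, income and the BSRI.

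**The concern.** A baseline self-report completed after a woman knows her arm may be shifted by that knowledge. If it is then used as a covariate, the adjusted difference moves although nothing real has changed. Completing T0 before website access protects T0 from contact with the programme, but not from knowledge of whether calls are coming.

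The partner question is one of selection. Invitation does not depend on arm, but no rule places an absent partner's consent before disclosure. If willingness to join depends on arm, the partners who join are no longer groups formed by randomisation.

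The gender-role point does not depend on the order of T0. A score built at 6 months is measured after the intervention and after the primary endpoint. Its components may themselves be changed by the intervention, and it is missing for women lost between T1 and T2.

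**Working it through.** **Order of events.** Side by side, the recruitment text gives: consent; telephone screen; randomisation and disclosure; T0 link to those already recruited; website access. Only the EPDS and the two exclusion screens are clearly measured before the arm is known.

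**What each analysis uses.**
- Primary chi-square: no baseline covariate, so not affected.
- EPDS ANCOVA: baseline EPDS comes from inclusion, so its covariate is not affected.
- GAD-7: affected only if the reference back to the EPDS model means each outcome's own baseline. That is an inference, because baseline EPDS is the only covariate named. By the individual timings, GAD-7 is the only continuous secondary scale besides the EPDS with both a T0 and a follow-up value. Substance use is also asked at both times, in a form not stated. The general lead line would widen this.
- Adjustment for imbalance: a T0 self-report such as PRAQ-R2 could enter, including in an adjusted logistic model of the primary outcome.
- Partner outcomes: affected only through uptake.

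**Plan's own figure.** For 20% against 10%, two-sided 5%, 80% power: n = [1.960·√(2·0.15·0.85) + 0.842·√(0.16 + 0.09)]² / 0.10² = 199 per arm. Then 199/0.80 gives 249 per arm (498 in total) and 199/0.81 gives 246 (492), against the stated 500. The sample size reproduces and this point does not alter it. With 10% attrition to 3 months, 500 × 0.9 / 2 = 225 per arm.

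**Illustration for GAD-7 (shift, correlation and carry-over are assumptions).** Let s be the T0 shift in one arm (SD), r the T0-T1 correlation and k the share of the shift that persists to T1. The size of the adjusted bias is |k − r|·s and of the unadjusted bias k·s. SE = √(2/225)·√(1 − r²). The detectable difference at two-sided 1% and 80% power is (2.576 + 0.842)·SE = 3.418·SE. With k = 0:

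| s | r | Bias | SE | Detectable | Bias/detectable | False-positive rate (nominal 1%) |
|---|---|---|---|---|---|---|
| 0.05 | 0.30 | 0.015 | 0.0899 | 0.307 | 5% | 1.1% |
| 0.10 | 0.45 | 0.045 | 0.0842 | 0.288 | 16% | about 2% |
| 0.20 | 0.60 | 0.120 | 0.0754 | 0.258 | 47% | 16% |

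The last column is P(|Z + bias/SE| > 2.576). The bottom row needs the largest shift, the highest correlation and no carry-over. In the middle row, k = 0.45 gives zero bias, and k = 1 gives 0.55 × 0.10 = 0.055 SD adjusted against 0.10 SD unadjusted.

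**Illustration for partners (uptake and selection are assumptions).** With uptake p and willingness-outcome correlation ρ, the mean among those who join is ρ·φ(z_p)/p. Uptake of 55% against 50% at ρ = 0.1 gives a spurious difference of 0.1 × (0.798 − 0.720) = 0.008 SD. Uptake of 70% against 50% at ρ = 0.3 gives 0.3 × (0.798 − 0.497) = 0.090 SD. Applying the women's 10% attrition to partners, the detectable differences are 0.445 and 0.422 SD, so these are 2% and 21% of them.

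**Gender-role score.** From the plan's attrition, 500 × 0.9 = 450 women have T1 data. At T2 there are 450 × 0.9 = 405, or 500 × 0.8 = 400. So 45 to 50 of the 450 (10-11%) would have no score.

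**The case against.** The strongest reply is that the order is not established. The T0 sentence closes a subsection that has already gone back to the recruitment call, so the text is arranged by topic as much as by time, and Figures 1 and 3 might settle the matter. This stands: the point is about what the prose allows.

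The GAD-7 route is also inferred. Baseline EPDS is the only covariate named and is available for every scale. If it is the one meant, the GAD-7 exposure disappears. This stands too.

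The contrast between arms at T0 is mild. "The control group will receive a fully automated version of the virtual intervention", so women differ only in knowing whether calls are coming. The plan itself calls imbalance unlikely, and the moderator work is exploratory and runs only if the intervention is found effective. All of this limits the reach but does not remove the opportunity for bias.

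Gender and a gender-role score may be different variables. If so, the text does not say so, and no baseline gender-role measure is described.

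A reader might go further and infer that the primary result is compromised. The documents do not support that: the EPDS is taken at inclusion and the primary test is unadjusted. Nor do they show that GAD-7 will be biased, since they give no shift, correlation or carry-over.

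**Conclusion.** The point holds as an opportunity for bias in secondary, tertiary and exploratory analyses, and as a mismatch in when the gender moderator is measured. Its severity is minor to moderate.

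The order rests on the prose alone. The GAD-7 exposure rests on reading the ANCOVA as using each outcome's own baseline. The bias figures are illustrations and other assumptions would give other values; the true bias may be zero, and its direction is not known beforehand. The firmest part is the gender-role score: whatever the order of T0, a 6-month score does not answer a question about a baseline moderator.

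**What to change.** State the order. Have the woman complete T0, online or by telephone as the plan already allows, before REDCap randomisation and disclosure, and recheck that she is still within 12-25 weeks' gestation. Name the baseline covariate for the secondary ANCOVAs.

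Seek partner consent and T0 in the same window where possible. Flag partners who join after disclosure, report uptake by arm, and report partner outcomes with and without them.

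Collect the gender-role items at T0 for the moderator analysis. Otherwise, state that they are a different variable from baseline gender and do not use the T2 score as a moderator.

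If the order cannot change, limit added covariates to the screening EPDS and fixed characteristics, and report GAD-7 with and without its T0 value. The version without it has less power: at r = 0.45 the detectable difference rises from 0.288 to 3.418 × √(2/225) = 0.322 SD, and power at 0.288 SD falls from 80% to 68%. Reordering is therefore preferable.

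**Cost.** REDCap steps are reordered, randomisation waits briefly, and T0 becomes slightly longer (the assessment tools currently "take only 15-30 minutes to complete"). Women who do not return T0 would not be randomised, which tilts the sample somewhat towards motivated women; under the order as it reads they would be randomised without a T0 value. If an assumed 5-15% do not return it, 500/0.95 − 500 = 26 to 500/0.85 − 500 = 88 more eligible women are needed. That is about 2-6 weeks at the later rate of 15 "women per week willing to accept randomization", or 5-18 weeks at the initial five per week. If T0 is in fact already completed before disclosure, one sentence saying so settles the covariate part; the timing of absent partners' consent still needs stating.

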During pregnancy and the postpartum period, women are at heightened risk of mental health problems, with 1/5 experiencing moderate to high levels of depressive symptoms (1, 2). Perinatal mental health problems often go unrecognized and undiagnosed (3), with fewer than 20% of symptomatic women receiving treatment (4). The cost of untreated maternal depression is estimated at over \$17,000 US per mother per year over the first five years of the child's life. In comparison, gestational diabetes costs up to \$3,300 per mother and occurs only during pregnancy (5). The consequences of untreated perinatal mood disorders include maternal psychological, social, occupational, and physical dysfunction (1, 2).

About 20-25% of pregnant women have subclinical levels of depression (Edinburgh Postnatal Depression Scale (EPDS) score 9-12) and 2/3 of these will go on to clinical postpartum depression (EPDS \geq 13) (6-8). Though ineligible for publicly funded clinical services, these women have poorer parenting/offspring outcomes (6). Fifteen meta-analyses (300+ studies) have documented associations between maternal depression and poor cognitive, behavioral, and emotional outcomes in the offspring, starting at birth and extending into adolescence (9-18). Preventive interventions and childhood assessments could inform the putatively causal role of maternal mental health on child development. In this study, we test an early pregnancy intervention and its impact on postpartum ages 3 and 6 months. The virtual or remote format of the intervention (online and telephone) is designed to overcome long-standing mental health management barriers.

Prevention of Postpartum Issues

There is growing evidence that the societal burden of perinatal mental health issues can be prevented. Most women with postpartum depression have symptoms during pregnancy (19, 20). High-risk women may be identified by simple screening (e.g., mobile phone) and EPDS (21), and prevention programs in person or in groups are effective (2). Recognizing potential for early prevention, the United States Preventive Services Task Force (2019) issued a level B recommendation “that clinicians provide or refer people who are at increased risk of perinatal depression to counseling interventions.” These include cognitive behavioral therapy (CBT) and interpersonal counseling, such as the existing, evidence-based *Mothers & Babies* program (22-25).

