Primary research question: Compared to a fully automated virtual (with a workbook or online material) intervention, what is the effect of the virtual intervention with telephone support for pregnant women with subclinical depressive symptoms on maternal depression at 3 months' postpartum? We adopted an indicated prevention strategy (targeted or secondary prevention), targeting women with symptoms of depression during pregnancy.

Secondary research questions: Compared to a fully automated virtual (with a workbook or online material) intervention, what is the effect of the virtual intervention with telephone support on: 1) maternal depression at 6 months' postpartum; 2) maternal anxiety, perceived stress, well-being, self-efficacy, self-compassion, sleep quality, tobacco, alcohol and drug usage, social functioning, social support, marital satisfaction, co-parenting and parental cognitions and practices, at 3 and 6 months' postpartum; 3) child's socioemotional development at ages 3 and 6 months; 4) maternal health care services utilization at 6 months' postpartum.

Tertiary research questions: What is the effect of a virtual intervention (with a workbook or online material) + telephone support on 1) partner depression, anxiety, perceived stress, well-being, self-efficacy, self-compassion, sleep quality, tobacco, alcohol and drug usage, social functioning, social support, marital satisfaction, co-parenting and parental cognitions and practices, at 3 and 6 months' postpartum; 2) What are the moderators of the effect (e.g., compliance to the intervention, COVID-19 infection of self or relatives, personality disorder traits, socioeconomic level, ethnicity, gender at the baseline, and sex of the child).

Method

[figure not shown]
Design

A randomized controlled trial (RCT) of 500 Quebec women with a 1:1 assignment to either virtual preventive intervention with telephone support or without telephone support (control). Figure 1 presents the trial design.

Population

French-speaking pregnant women older than 14 years old, with subclinical levels of depression (EPDS 9-12).

Figure 1. Trial design

Pregnant Women Recruitment

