We followed the USPSTF recommendation for the prevention of postpartum depression (2) by targeting pregnant women with moderate depressive symptoms, who could reasonably be considered as signaling distress or early signs of illness, are at high risk for postpartum depression, and are not eligible for specialized psychiatric care. Our program is a virtual and population-based preventive intervention, not a treatment for clinical depression, although it could reasonably be conceived as an adjuvant to psychiatric care.

Pregnant women inclusion criteria: Pregnant women (12-25 weeks' gestation), ages 14 years or older, with: 1) subclinical levels of depression (EPDS scores 9-12) and 2) ability to read and understand French.

Pregnant women exclusion criteria: 1) EPDS score in the clinical range (≥ 13) or no symptoms (EPDS < 9); 2) Positive screening of psychotic symptoms using the Psychosis Screening Questionnaire (PSQ); 3) self-reported substance abuse problems. These criteria are consistent with those of other prevention trials (51).

Partners inclusion criteria: 1) The spouse or any other significant person who will accompany the pregnant woman during pregnancy and after childbirth, chosen by the pregnant woman. 2) The pregnant woman has consented to participate in the study.

Participant allocation. Randomization will be centrally controlled by the CHU Ste-Justine Applied Clinical Research Unit (URCA), headed by co-PI [name]. An independent biostatistician will create the randomization scheme, a computer-generated random listing using a 1:1 allocation, according to trial statistician instructions. Random permuted blocks randomization will be used. The randomization list will be WEB-based and completed via REDCap.

Bias protection. With detailed informed consent procedures, it is expected that pregnant women will accept their randomized group allocation. The intervention team will be blinded to the initial level of depressive symptoms. No formal virtual depression prevention intervention program yet exists in Quebec. There will be no interference with usual medical/nursing care, which may include antidepressant medication and/or psychotherapy.

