Sample size. A meta-analysis of 58 studies indicates that the overall prevalence of postpartum depression is 17% (95% CI: 0.15–0.20) (53). This estimate falls within previously published estimates of 13%–19.2% (54, 55) and is similar to Hahn-Holbrook's 2018 finding of 17.7%. In-person interventions using the *Mother & Babies* course reported moderate effect sizes (OR = 0.28 (0.08-0.94) (22) and OR = 0.45 (0.19-1.10) (24)). Fully web-based without nurse-based telephone support reported small to moderate effect sizes (40). Given that the proposed intervention is offered virtually with nurse-based telephone support, we calculated a sample size that allows us to detect a moderate decrease in rates of clinical depression. We anticipate that 20% of pregnant women in the control group will have an EPDS score ≥ 13 at postpartum. A total of 500 pregnant women (250 per arm) is needed to detect an absolute reduction of 10% (i.e., 20% of women with EPDS ≥ 13 in the control arm versus 10% in the intervention arm) with 80% of power and a 2-tailed alpha of 5%. The sample size includes an attrition rate of 10% for 3 months' postpartum and another 10% between 3 and 6 months' postpartum. Based on our experience with pregnant women and the intervention (see Section about Pilot Study), the 10% attrition estimate is conservative. As most of the secondary

outcomes are continuous, the sample size provides enough power to detect small to moderate effect sizes using a 2-tailed alpha of 1% to account for multiple tests.

Compliance. We conducted a feasibility pilot study including 17 pregnant women. All began to read the online material and 2 refused further participation after 2 telephone calls, a dropout rate of 11.7%. We therefore expect that 80-90% of the intervention group will read at least some of the intervention material. Intervention compliance will be defined as completion of a minimum of 6/8 online modules and 6/10 telephone follow-ups. Compliance will be monitored automatically online and by nurses during telephone calls. Weekly text reminders will be sent out to maximize compliance (see details in Appendix H).

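### Is the planned 20% control-arm rate of EPDS ≥ 13 too low for women enrolled because their EPDS is 9–12?

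*Combined protocol and SAP*

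**What the plan says.** The Sample size section first cites a meta-analysis in which the "overall prevalence of postpartum depression is 17" per cent (95% CI 15–20%), with other published estimates of 13–19.2% and 17.7%. It then gives two odds ratios for the in-person version of the course, 0.28 and 0.45, and notes small to moderate effects for web programmes without telephone support. The planning rate follows: "We anticipate that 20% of pregnant women in the control group will have an EPDS score ≥ 13 at postpartum". The total of 500, 250 per arm, "is needed to detect an absolute reduction of 10" percentage points (20% versus 10%) with 80% power at a two-sided 5% level. It allows for 10% attrition by 3 months and another 10% by 6 months.

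The trial population is narrower than the one behind those prevalences. The Population section limits it to women "with subclinical levels of depression (EPDS 9-12"), and the inclusion criteria repeat "subclinical levels of depression (EPDS scores 9-12"). The Sample section says that these women "are at high risk for postpartum depression". The opening background puts 20–25% of pregnant women in this EPDS band, "and 2/3 of these will go on to clinical postpartum depression" (EPDS ≥ 13).

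The control arm is not untreated. It receives the fully automated version of the programme, and under Bias protection usual care continues, "which may include antidepressant medication and/or psychotherapy".

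**The concern.** A control rate should describe the women who will be randomised, under the control condition, at the time of the primary outcome. Here the rates cited just before the 20% describe postpartum women in general. The 20% is only a little above them and less than a third of the protocol's own figure for the enrolled group. No section says why 20% is expected in EPDS 9–12 women on the automated programme at 3 months.

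The 80% power claim for the primary comparison rests on this rate. The target is stated as an absolute difference, and a fixed 10-point difference becomes harder to detect as the control rate rises from 20% towards 50%. If the true rate were well above 20%, a non-significant result would be weaker evidence against a 10-point benefit of telephone support than the protocol implies.

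**Working it through.** **Inputs.** From Sample size: p1 = 0.20, p2 = 0.10, two-sided alpha 0.05 (z = 1.960), power 80% (z = 0.842), 250 per arm, attrition 10% + 10%. From Primary outcome: assessment at 3 months. Evaluable at 3 months: 250 × 0.90 = 225 per arm.

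**1. Reproduce the plan's figure.** Pooled-variance two-proportion formula, no continuity correction, p̄ = (p1 + p2)/2:

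n = [1.960·√(2p̄(1−p̄)) + 0.842·√(p1(1−p1) + p2(1−p2))]² / (p1−p2)²

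With p̄ = 0.15 this gives 199 per arm. With 20% attrition, 199/0.80 = 248.75, so 249 per arm and 498 in total. With compounded attrition, 199/0.81 = 245.7, so 246 per arm and 492 in total. The stated 500 reproduces.

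**2. Power at 3 months under the plan's rates.**

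Power = Φ{[|p1−p2|·√n − 1.960·√(2p̄(1−p̄))] / √(p1(1−p1) + p2(1−p2))}

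= Φ{[0.10 × 15 − 0.990]/0.50} = Φ(1.02) = 84.6%.

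**3. Vary the control rate, 225 per arm.** The rates above 20% are assumptions. The 20% versus 10% target implies an odds ratio of (0.10/0.90)/(0.20/0.80) = 0.444 and a relative risk of 0.50.

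| Control rate | 10-point reduction | Odds ratio 0.444 | Relative risk 0.50 |
|---|---|---|---|
| 20% | 84.6% | 84.6% | 84.6% |
| 22.5% | 79.9% | 88.1% | 89.3% |
| 25% | 75.7% | 90.8% | 92.7% |
| 30% | 68.9% | 94.4% | 97.0% |
| 40% | 60.5% | 97.7% | 99.7% |

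The first column crosses 80% at a control rate of 22.5%. The reduction detectable with 80% power is 9.5 points at 20%, 10.5 at 25%, 11.3 at 30% and 12.5 at 40%.

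**4. Which scale does the protocol's evidence use?** Its only numerical effects are odds ratios. Applying 0.45 to a 20% control rate: odds 0.25 × 0.45 = 0.1125, and 0.1125/1.1125 = 10.1%. That is almost exactly the planned 10%. The protocol does not say the target was derived this way; this is an inference.

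**5. Is two thirds a usable planning rate?** The background puts 20–25% of pregnant women at EPDS 9–12; Planned recruitment rate reports 374/1695 = 22.1%. Two thirds of 20–25% is 13.3–16.7% of all pregnant women. Against the cited overall prevalence of 17%, this leaves 17 − 16.7 = 0.3 to 17 − 13.3 = 3.7 points for everyone else, including women already at EPDS ≥ 13 in pregnancy. At the upper confidence limit of 20% it leaves 3.3 to 6.7 points. Read as a rate at one time point, two thirds fits poorly with the protocol's other figures. It may be cumulative or defined differently; the text gives no time point or treatment condition.

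**The case for a change.** The best case for a change is that the automated control programme cannot plausibly bridge the gap. Going from 2/3 (odds 2.0) to 20% (odds 0.25) needs an odds ratio of 0.25/2.0 = 0.125. The in-person odds ratios of 0.28 and 0.45 would bring 2/3 down only to 35.9% and 47.4%, and the protocol credits automated programmes with small to moderate effects. Its section on virtual interventions also reports that, in a large trial of such a programme, the benefit was gone by 3 and 6 months. The absolute scale is the protocol's own choice, and the margin before power for 10 points drops below 80% is only 2.5 percentage points.

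Part of this stands. The reasoning behind 20% is not written down, and the consistency check on the two thirds casts doubt on that figure without supplying a source for the 20%. But the bridging argument works only if two thirds is the untreated rate at 3 months, which the documents do not say. The 20% exceeds every point estimate cited and equals the upper confidence limit of the 17%. A modest uplift for higher risk, partly offset by an active control and continuing usual care, is coherent though unstated. Holding 10 points fixed while the control rate rises also assumes a weaker relative effect: the odds ratio goes from 0.44 at 20% to 0.53 at 25% and 0.64 at 40%. The loss of power comes from that assumption as much as from the rate.

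**Conclusion.** No change to the plan follows. This is a gap in explanation around a correctly computed, explicitly conditional power statement. The 500 reproduces (498 or 492, depending on how attrition is combined), and power at the primary time point is 84.6% under the stated rates. The documents do not show that 20% is wrong, and the two-thirds figure may be the less reliable of the two.

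A higher control rate would not by itself leave the trial underpowered. Over control rates of 20–40%, power for a fixed 10-point reduction runs from 84.6% down to 60.5%; for a constant odds ratio of 0.44 it runs from 84.6% up to 97.7%. Stating a source for the 20%, or a time point for the two thirds, would help a reader, but would alter neither the sample size, the design, the analysis nor any conclusion. At analysis, the observed control rate and the confidence interval for the difference in proportions will show what reduction a null result excludes, whatever rate was assumed at planning.

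This rests on 225 evaluable women per arm (10% attrition by 3 months), the pooled two-proportion approximation without continuity correction, and assumed control rates above 20%.
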